## PROTOCOL

### Neurosteroids as Novel Therapeutic Agents for PTSD in OEF/OIF/OND Veterans

PI: [name], PhD

on anticipated collinearities between the dichotomous randomization proxy and change, models will initially be estimated without the former. A significant inverse association between change in steroid levels and change in CAPS-5 scores would support the hypothesized efficacy of DHEA as an adjunctive therapy in treating PTSD. As above, results would be corrected for multiple comparisons.

Tests of secondary measures will be conducted as described above. Thus, proposed measures will be regressed as change from baseline scores on a model controlling for the baseline level of the tested outcome measure, the dichotomous randomization proxy, and an interaction term crossing the latter with time. Tests will again be based on a 1 df test of the estimated contrast (LSME: see above) of the difference between drug and placebo at the final time point. Expectations are that change in adverse outcome measures will be significantly mitigated in the DHEA intervention arm; measures associated with salubrious outcomes will be, conversely, improved. All results will be adjusted for multiple comparisons.

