Change in total DSM5-defined PTSD symptoms from pre- to post- treatment, as assessed by the CAPS-5, the gold standard method for assessing PTSD symptoms in pharmacological treatment trials; measurements will be gathered at two-week intervals beginning at baseline and continuing through Week 8. Measures of pre-post treatment differences at the four study intervals will be regressed on a dichotomous proxy measure denoting treatment status coded positive for subjects randomized to the DHEA condition. In addition to the treatment proxy, all models will include covariates for measurement interval (time), and an interaction term crossing the treatment proxy with time. Test of the secondary hypothesis will be based on a 1 df test of the contrast of difference between drug and placebo at the final time point (SAS: LSMESTIMATE statement). Specifically at Week 8, H0: LSMEdhea  $\geq$  LSMEplacebo versus Ha: LSMEdhea  $<$  LSMEplacebo. We hypothesize rejection of a null hypothesis positing that difference in PTSD symptoms from baseline will be equivalent or greater among subjects randomized to DHEA at the final time point in lieu of an alternative hypothesis positing a reduction in PTSD symptoms in the DHEA cohort relative to placebo.

Measures of serum levels of three neurosteroids: DHEA, DHEAS, and androsterone will also be analyzed. As above, the outcome measure will be the change in steroid level from baseline (i.e., following 2 week placebo lead in) to Week 8 with measurements at two-week intervals. Models will be estimated as described above with tests of the primary hypothesis based on a 1 df test of the estimated contrast of the difference between drug and placebo at the final time point. In all cases, the following hypothesis will be tested: H0: LSMEdhea  $\leq$  LSMEplacebo versus Ha: LSMEdhea  $>$  LSMEplacebo. Results for tests of Aim 2 will be adjusted for multiple comparisons using the method of Hochberg (1998).

As secondary test of the hypothesized association between change in PTSD status and change in neurosteroid levels, Week 8 changes CAPS-5 scores will be regressed on Week 8 change in neurosteroid levels. Models will include, as above, covariates for age, gender, smoking status, depression, TBI status, and a measure of the baseline level of the tested neurosteroid. Based

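### The plan counts an inverse slope of CAPS-5 change on neurosteroid change as support for DHEA efficacy, but that slope is not a valid test of efficacy

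*Combined protocol and SAP*

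**What the plan says.** All of this stands in Data Analysis and Statistical Considerations.

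- **The efficacy test.** For CAPS-5, "Test of the secondary hypothesis will be based on a 1 df test of the contrast of difference between drug and placebo", evaluated at Week 8, with "an alternative hypothesis positing a reduction in PTSD symptoms in the DHEA cohort relative to placebo". This comparison is randomised and directional.
- **The regression.** It is introduced with the words "As secondary test of the hypothesized association between change in PTSD status and change in neurosteroid levels", and specifies that "Week 8 changes CAPS-5 scores will be regressed on Week 8 change in neurosteroid levels". The covariates are age, gender, smoking, depression, TBI status and the baseline level of the steroid concerned.
- **The treatment term.** Based "on anticipated collinearities between the dichotomous randomization proxy and change, models will initially be estimated without the former". The first models therefore pool both arms.
- **The reading.** "A significant inverse association between change in steroid levels and change in CAPS-5 scores would support the hypothesized efficacy of DHEA".
- **Multiplicity.** "As above, results would be corrected for multiple comparisons".

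The efficacy reading is not made conditional on the randomised contrast.

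**The concern.** The plan already has a valid test of whether DHEA lowers CAPS-5. The quoted sentence opens a second route to the same conclusion through a slope that answers a different question.

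Steroid change at Week 8 varies for two reasons. One is allocation, which is randomised. The other is everything that makes participants differ within an arm, which is not. The protocol itself suggests how a within-arm link with symptoms could exist without a drug effect:

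- Background and Significance reports lower DHEAS in Veterans with PTSD and a positive association of DHEAS with resilience. These are endogenous links.
- Potential Difficulties and Limitations uses serum DHEA and DHEAS as a compliance marker in the DHEA arm.
- Potential Risks allows dose reduction for side effects, so exposure depends partly on events after randomisation.

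Compliance and baseline CAPS-5 are not among the regression's listed covariates. A correction for multiple comparisons does not address confounding.

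Two misreadings follow. If the contrast is not significant, a significant slope could be reported as support for efficacy. If the contrast is significant, the same arm difference could be counted twice.

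**Working it through.** The plan gives no effect size, SD or power for this regression, so there is no figure to reproduce.

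**Inputs from the documents.** About 16 participants per arm (Design), six covariates and alpha 0.05 (Data Analysis and Statistical Considerations).

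**Inputs assumed.** Separation D between arms in steroid change, in within-arm SD; inverse within-arm correlation of size r; two-sided slope test; one-sided 0.05 contrast (my reading of the directional hypotheses), simplified to an unadjusted t-test; equal within-arm steroid SD unless stated.

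**Step 1: what the pooled slope estimates.** With equal arms and variances and covariates ignored,

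pooled slope = w × (arm difference in CAPS-5 change ÷ D) + (1 − w) × within-arm slope, where w = (D²/4) ÷ (1 + D²/4).

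- D = 2: w = 1/2 = 0.50
- D = 4: w = 4/5 = 0.80
- D = 6: w = 9/10 = 0.90

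With no drug effect the first term is zero. At r = 0.5 the within-arm slope is −0.5, so the expected pooled slope is 0.50 × (−0.5) = −0.25 at 2 SD, 0.20 × (−0.5) = −0.10 at 4 SD and 0.10 × (−0.5) = −0.05 at 6 SD. It is not zero, although the drug does nothing.

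**Step 2: how often it is significant and inverse.** Least squares with six noise covariates leaves 32 − 8 = 24 residual df. The simulations used 20,000 replicates per setting. The nominal inverse-tail rate is 2.5%, or 0.05 ÷ 3 ÷ 2 = 0.8% with Bonferroni for three steroids. All rows assume no drug effect.

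| Result | 2 SD | 4 SD |
|---|---|---|
| Pooled slope, r = 0.5 | 42% | 19% |
| Same, Bonferroni | 26% | 9% |
| Slope significant, contrast not, r = 0.5 | 38% | 14% |
| Same, Bonferroni | 22% | 5% |
| Same, Bonferroni, placebo SD 0.2 of DHEA SD | 6-8% | 1-2% |
| Pooled slope, r = 0.3 | 17% | 9% |
| Pooled slope, r = 0 | nominal | nominal |

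At 6 SD with equal variances and r = 0.5, the uncorrected pooled rate is about 11%. The contrast itself rejects at about its nominal 5%.

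**Step 3: adding the treatment term.** The slope is then wholly within-arm. At r = 0.5 it is significant and inverse in about 75% of trials with no drug effect, and also in about 75% with a drug effect of 0.8 SD. It carries no information on whether the drug works.

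**Step 4: a working drug with no within-arm link.** At an effect of 0.8 SD and D = 4, the pooled slope is significant in 41% of trials and the contrast in 72%. The slope is significant in 55% of the trials where the contrast is significant, and in about 5% of those where it is not. Here it is a weaker restatement of the contrast, not a false claim.

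**The case against.** The strongest reply is that the plan already keeps the two questions apart. The regression is introduced as a secondary test of association and the CAPS-5 hypothesis is tested by the randomised contrast. Tertiary Outcome Measures lists correlation of neurosteroids with rating scales, and Study Interventions treats the steroids as candidate biomarkers. Support is a mild word in a pilot whose primary outcome is fMRI. The plan expects collinearity, hence wide separation, and there the slope is mostly the randomised difference. A within-arm correlation of 0.5 with an inert drug is an assumption. The rule withdrawing patients below 80% compliance narrows one route to it. Unequal variances are plausible because only one arm is dosed, and they reduce the rates sharply.

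Much of this stands, and it limits the size of the point. It does not remove the sentence: none of those places says that the slope should not be read as evidence of efficacy.

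Two stronger readings are tempting, and the material does not support either.

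- A reader might infer that the slope contains no randomised information. It does: at 4 SD, 80% of the steroid variance lies between arms, and with neither a drug effect nor a within-arm link the test is nominal.
- A reader might infer from the 75% in step 3 that adjusting for arm creates errors when the drug is inert. That figure is power to detect a real within-arm association, and it is the same whether or not the drug works. The error lies only in calling the result efficacy.

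**Conclusion.** The concern holds as a point about interpretation. A significant inverse slope can arise with no drug effect, and neither the multiplicity correction nor a treatment term makes it a valid test of efficacy. Under the equal-variance assumptions with r = 0.5, the corrected slope would give support without a significant contrast in about 5% (4 SD) to 22% (2 SD) of trials. The figure is a few percent or less under wide separation with unequal variances. Every rate depends on separation, correlation and SD ratio, none of which the documents give.

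The point is minor. A reader might infer that the trial's CAPS-5 efficacy test is compromised; it is not, because the randomised contrast stands on its own. A reader might also take the unwritten follow-on model, implied by fitting without treatment at first, as a separate flaw. The covariate list and the one named omitted term let it be inferred, so this is missing detail only.

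**What to change.** Delete the sentence saying that an inverse association would support efficacy. State that CAPS-5 efficacy rests only on the randomised Week 8 contrast, and label the regression as exploratory evidence of association. This changes wording only and needs no new data, participants or procedures.

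Optionally, report the treatment-adjusted slope with its confidence interval beside the pooled slope, and draw no efficacy conclusion from either. The cost is precision. At an assumed 4 SD separation the variance inflation factor is 1 ÷ (1 − 0.80) = 5, and the mean simulated 95% half-width rises from 0.18 to 0.43 CAPS-5 SD per steroid SD.

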## PROTOCOL

Neurosteroids as Novel Therapeutic Agents for PTSD in OEF/OIF/OND Veterans  
PI: [name], PhD

### Appendix A: Expedited Review of Research

The categories of research that may be reviewed by the IRB through the expedited review procedure include research activities that present no more than minimal risk to human subjects **AND** involve procedures listed in one or more of the specific categories listed below.

The expedited review procedure is not to be used when identification of the subjects or their responses would reasonably place them at risk of criminal or civil liability; be damaging to the subjects' financial standing, employability, insurability, or reputation; or be stigmatizing, unless reasonable and appropriate protections are implemented so that risks related to invasion of privacy and breach of confidentiality are no greater than minimal. The IRB must apply the standard requirements for informed consent (or its waiver, alteration, or exception) to all studies that undergo expedited review.

EXPEDITE CATEGORIES	
1-Drugs and Devices: One of the following must be met:	(1) The research is on drugs for which an IND application is not required. (2) The research is on medical devices for which an investigational device exemption (IDE) application is not required; or the medical device is cleared or approved for marketing, and the medical device is being used in accordance with its cleared or approved labeling.
2-Blood Samples: Collected by finger / heel / ear stick or venipuncture:	(1) From healthy, nonpregnant adults who weigh at least 110 pounds. For these subjects, the amounts drawn may not exceed 550 milliliters (ml) in an 8-week period, and collection may not occur more frequently than two times per week; or (2) From other adults and children, considering the age, weight, and health of the subjects, the collection procedure, the amount of blood to be collected, and the frequency with which it will be collected. For these subjects, the amount drawn may not exceed the lesser of 50 ml or 3 ml per kilogram (kg) in an 8-week period, and collection may not occur more frequently than two times per week.
3-Noninvasive Collection of Biological Specimens: Collected prospectively for research purposes by noninvasive means:	(1) Hair and nail clippings in a non-disfiguring manner. (2) Deciduous teeth at time of exfoliation or if routine patient care indicates a need for extraction. (3) Permanent teeth if routine patient care indicates a need for extraction. (4) Excreta and external secretions (including sweat). (5) Uncannulated saliva collected either in an unstimulated fashion or stimulated by chewing gumbase or wax or by applying a dilute citric solution to the tongue. (6) Placenta removed at delivery. (7) Amniotic fluid obtained at the time of rupture of the membrane prior to, or during, labor. (8) Supra- and subgingival dental plaque and calculus, provided the collection procedure is not more invasive than routine prophylactic scaling of the teeth and the process is accomplished in accordance with accepted prophylactic techniques. (9) Mucosal and skin cells collected by buccal scraping or swab, skin swab, or mouth washings. (10) Sputum collected after saline mist nebulization.

## PROTOCOL

### Neurosteroids as Novel Therapeutic Agents for PTSD in OEF/OIF/OND Veterans

PI: [name], PhD

#### EXPEDITE CATEGORIES

**4-Noninvasive Collection of Data:** Data must be collected through noninvasive procedures (not involving general anesthesia or sedation) routinely employed in clinical practice, excluding procedures involving x-rays or microwaves.

(1) Physical sensors that are applied either to the surface of the body or at a distance and do not involve input of significant amounts of energy into the subject or an invasion of the subject's privacy.

(2) Weighing the subject.

(3) Testing sensory acuity.

(4) Magnetic resonance imaging (MRI).

(5) Electrocardiography, electroencephalography, thermography, detection of naturally occurring radioactivity, electroretinography, ultrasound, diagnostic infrared imaging, Doppler blood flow, and echocardiography.

(6) Moderate exercise, muscular strength testing, body composition assessment, and flexibility testing, where appropriate, given the age, weight, and health of the individual.

**5-Collected Material:** Research involves:

(1) Materials (data, documents, records, or specimens) that have been collected for any purpose, including previous research; or

(2) Materials (data, documents, records, or specimens) that will be collected solely for nonresearch purposes (such as medical treatment or diagnosis).

**6-Collection of Data From Voice, Video, or Photographs:** Research involves collection of data from voice, video, or photographs.

**7-Group Characteristics, Surveys, Interviews, and Quality Assurance:** Research must be on individual or group characteristics or behavior (including, but not limited to: research on perception, cognition, motivation, identity, language, communication, cultural beliefs or practices, and social behavior), or will employ survey, interview, oral history, focus group, program evaluation, human factors evaluation, or quality assurance methodologies. **NOTE:** *Some research in this category may be exempt from the VA regulations for the protection of human subjects (38 CFR 16.101(b)(2) and (b)(3)). This listing refers only to research that is not exempt.*
